3.2.2.5 Validation

The individual medical tests described above have been included both for their utility in measuring general health and health conditions associated with exposure to the CoCs, as well as for purposes of validation. That is, specific medical tests also can be used as objective measures to validate reported medical health information from the health

questionnaire that is subjective in nature (Moffat et al., 2000; Smith- Sivertsen et al., 2000).

Medical tests that will serve as validators in this study include:

- Bilirubin test: validates the jaundice question in the questionnaire,
- Plasma cotinine test: validates recent smoking history question in the questionnaire,
- Serum TSH and fT4 test: validates thyroid condition questions in untreated individuals,
- ECG test: validates history of heart attack question in the health questionnaire,
- CO breath test: validates recent smoking history question in the health questionnaire,
- FEV1/FVC/PEFR tests: help to validate chronic bronchitis, emphysema, chronic obstructive pulmonary disease, asthma and other respiratory questions from the health questionnaire, and
- Skin patch tests: validates contact dermatitis question from the health questionnaire.

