4.2.2.1 Questionnaire development and internal testing

Questions from the demographic section of the questionnaire were derived from the CCHS. Most of the questions collecting exposure information were developed under the advisement of experts in the areas of toxicology and environmental health and safety.

Questions pertaining to the smoking of cigarettes and consumption of alcohol were borrowed from the CCHS. The questions that assess quality of life came directly from the HRQOL-4 questionnaire that was developed by the CDC. There are five symptom questions within the section of the questionnaire that collects information on current medical health status. These questions were used in the work done by Smith-Sivertsen and colleagues (2000). The rest of the health related questions come from the CCHS, with a few exceptions for health outcomes of particular interest for this study. Finally, all questions on drug use and mental health again come from the CCHS.

The only identifying information collected in this questionnaire is the individual's name and date of birth. This information will be entered into the data entry application and will only be used for identifying individuals if they request their data. Otherwise, all identifying information will be permanently removed before any analyses take place.

During the development of the health questionnaire, wording was not modified for the CCHS-derived health questions, the HRQOL-4 questions, or the questions borrowed from the research done by Smith-Sivertsen et al. (2000). These are pre-existing, validated questions that require consistent phrasing so as to allow for comparisons with other datasets.

Once the health questionnaire has been finalized, questionnaires will be prepared for pre-testing. This pre-testing will also allow for data entry, handling, and analyses procedures

to be checked, and thus they will need to be in place prior to the pre-testing. The questionnaire will be pre-tested while interviewer training proceeds.

During the pre-test, the interview team will duplicate as closely as possible the procedures that will take place during the administration/fielding of the final questionnaire. While the pre-test is being conducted, progress will be closely monitored, noting and addressing any problems that arise in terms of the content or administration of the questionnaire, or the data management and analyses process.

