Now thinking about your mental health, which includes stress, depression, and problems with emotions, for how many days during the past 30 days was your mental health not good?

_____ days

4. Recent Activity Limitation 

During the past 30 days for about how many days did poor physical or mental health keep you from doing your usual activities, such as self-care, work, or recreation?

_____ days

Current Medical Health Status

“We’d like to ask about certain chronic health conditions which you may have. We are interested in ‘long-term conditions’ that have lasted or are expected to last 6 months or more and that have been diagnosed by a health professional.” 

Respiratory:

1. Do you usually cough or clear your throat in the morning? 
 - Yes
 - No
 - Don’t Know, Refused

2. Do you cough on most days for at least 3 months of the year? 
 - Yes
 - No
 - Don’t Know, Refused

3. Do you bring up phlegm on most days for at least 3 months of the year? 
 - Yes
 - No
 - Don’t Know, Refused

4. Are you breathless when you climb two flights of stairs at an ordinary pace? 
 - Yes
 - No
 - Don’t Know, Refused

5. Are you breathless when at rest? 
 - Yes
 - No
 - Don’t Know, Refused

6. Do you have Chronic Bronchitis? 
 - Yes
 - No (Go to Q8)
 - Don’t Know, Refused (Go to Q8)

7. How old were you when this was first diagnosed? 
 - ____ Age in years
 - (MIN: 0) (MAX: current age)

8. Do you have Emphysema or Chronic Obstructive Pulmonary Disease? 
 - Yes
 - No (Go to Q10)
 - Don’t Know, Refused (Go to Q10)

9. How old were you when this was first diagnosed? 
____ Age in years
(MIN: 0) (MAX: current age)
10. Do you have food allergies? 
Yes
No (Go to Q12)
Don't Know, Refused (Go to Q12)
11. How old were you when this was first diagnosed? 
____ Age in years
(MIN: 0) (MAX: current age)
12. Do you have any other allergies? 
Yes
No (Go to Q14)
Don't Know, Refused (Go to Q14)
13. How old were you when this was first diagnosed? 
____ Age in years
(MIN: 0) (MAX: current age)
14. Do you have asthma? 
Yes
No (Go to Q17)
Don't Know, Refused (Go to Q17)
15. Have you had any asthma symptoms or asthma attacks in the past 12 months? 
Yes
No
16. In the past 12 months, have you taken any medicine for asthma such as, inhaler, nebulizers, pills, liquids, or injections? 
Yes
No

Upper Airway

17. Do you have an upper airway condition?
Yes
No (Go to Q20)
Don't Know, Refused (Go to Q20)

18. What type of upper airway condition do you have:
INTERVIEWER: Mark all that apply.

- Sinusitis

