- Rhinitis
- Nasal Polyps
- Nasal Septal Ulceration
- Other, Please specify

19. How old were you when this was first diagnosed?

_____ Age in years
(MIN: 0) (MAX: current age)

Skin:

20. Do you have a skin condition?

- Yes
- No (Go to Q23)
- Don't Know, Refused (Go to Q23)

21. What type of skin condition do you have:

INTERVIEWER: Mark all that apply.

- 1 Dermatitis/eczema
- 2 Pigmentation change (skin darkening or lightening; "change in skin color")
- 3 Hyperkeratosis (skin thickening)
- 4 Other, Please specify

22. How old were you when this was first diagnosed?

_____ Age in years
(MIN: 0) (MAX: current age)

Cardiovascular:

23. Do you have high blood pressure? 

- Yes
- No (Go to Q25)
- Don't Know, Refused (Go to Q25)

24. How old were you when this was first diagnosed? 

_____ Age in years
(MIN: 0) (MAX: current age)

Remember, we're interested in conditions diagnosed by a health professional.

25. Do you have migraine headaches? 

Yes

No (Go to Q27)

Don't Know, Refused (Go to Q27)

26. How old were you when this was first diagnosed? 

____ Age in years

(MIN: 0) (MAX: current age)

27. Do you have heart disease? 

Yes

No (Go to Q29)

Don't Know, Refused (Go to Q29)

28. How old were you when this was first diagnosed? 

____ Age in years

(MIN: 0) (MAX: current age)

29. Have you ever had a heart attack (damage to the heart muscle)? 

Yes

No (Go to Q30)

30. Do you currently have angina (chest pain, chest tightness)? 

Yes

No (Go to Q31)

31. Do you currently have congestive heart failure (inadequate heart beat, fluid build-up in the lungs or legs)? 

Yes

No (Go to Q32)

Thyroid:

32. Do you have a thyroid condition? 

Yes

No (Go to Q34)

DK, R (Go to Q34)

33. How old were you when this was first diagnosed? 

____ Age in years

(MIN: 0) (MAX: current age)

Gastro-intestinal/Liver:

34. Do you have stomach or intestinal ulcers? 

Yes

No (Go to Q36)

DK, R (Go to Q36)

35. How old were you when this was first diagnosed? 

____ Age in years

(MIN: 0) (MAX: current age)

36. Do you have Gastroenteritis?

Yes

No (Go to Q38)

DK, R (Go to Q38)

37. How old were you when this was first diagnosed?

____ Age in years

(MIN: 0) (MAX: current age)

38. Do you have Jaundice?

Yes

No (Go to Q40)

DK, R (Go to Q40)

39. How old were you when this was first diagnosed?

____ Age in years

(MIN: 0) (MAX: current age)

Neurological:

40. Do you have Peripheral Neuropathy (numbness or tingling in fingers or toes)?

Yes

No (Go to Q42)

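### The diagnosed-and-six-months lead-in is read directly before five respiratory symptom questions that need no diagnosis, and may push some true 'Yes' answers to 'No'

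*Protocol*

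**What the plan says.** Appendix 10.1 begins the Current Medical Health Status section with a lead-in for the interviewer to read. It restricts interest to long-term conditions "that have lasted or are expected to last 6 months or more and that have been diagnosed by a health professional". The next line is the Respiratory subheading, and the first item is "Do you usually cough or clear your throat in the morning". No new lead-in comes between them. Q2 asks "Do you cough on most days for at least 3 months of the year", Q3 asks the same about phlegm, and Q4 and Q5 ask about breathlessness. The first item naming a disease is Q6, chronic bronchitis.

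Section 4.2.2.1 describes these items: "There are five symptom questions within the section of the questionnaire that collects information on current medical health status". It says that they were used in a published study of airway symptoms and that their wording was not altered. On the borrowed questions generally it says: "These are pre-existing, validated questions that require consistent phrasing so as to allow for comparisons with other datasets". Section 6.2.1.4 lists symptomatology, alongside the presence and duration of disease, as content of the section. Sections 6.3 and 6.3.3 name the symptom study as a source of comparison data.

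**The concern.** The lead-in and the items define different targets. The lead-in asks for diagnosed, long-lasting conditions. Q1-Q5 ask whether the person coughs, brings up phlegm or is breathless. A resident with a daily cough and no diagnosis fits the item but not the lead-in, and nothing in the protocol says which prevails for these five questions.

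The lead-in can only narrow what counts, so any effect moves a true 'Yes' to 'No'. The items were borrowed so that results could be set beside the source study. A frame of diagnosed chronic disease placed over them can weaken that comparison even though no word of the items has changed. This is a property of the interview, so no later analysis can recover the lost answers.

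**Working it through.** The protocol gives no figure for these items, so there is nothing to reproduce. The check is a comparison of texts, followed by algebra for the direction of the bias.

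**Texts side by side (Appendix 10.1)**

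| Feature | Lead-in | Q1-Q5 |
|---|---|---|
| Target | long-term condition | symptom |
| Diagnosis by a health professional | required | not mentioned |
| Time criterion | 6 months or more, actual or expected | 3 months of the year (Q2, Q3); present tense (Q1, Q4, Q5) |
| Skip rule into or out of the items | none | none; every respondent is asked |

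The diagnosis requirement is the sharper conflict. The time criteria are not strictly incompatible, because a cough that returns every year can satisfy both. Later in the section, before the migraine item (Q25), the interviewer repeats the diagnosis requirement. The questionnaire thus treats the lead-in as a rule that carries forward over many items.

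**Direction.** Let p be the true symptom prevalence and s the share of symptomatic people who answer 'No' because of the lead-in. Assume that nobody without symptoms answers 'Yes'. Then:

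observed prevalence = p(1 - s)

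This never exceeds p. The documents give neither p nor s, so the values below are assumed. With p = 20%:

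| s | Observed prevalence |
|---|---|
| 0% | 20% |
| 10% | 20% × 0.90 = 18% |
| 30% | 20% × 0.70 = 14% |
| 50% | 20% × 0.50 = 10% |

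One way to build s is as the undiagnosed share times the share who take the lead-in literally. If 30% to 70% are undiagnosed and half of those take it literally, s is 0.5 × 0.3 = 15% to 0.5 × 0.7 = 35%. Observed prevalence is then 20% × 0.85 = 17% down to 20% × 0.65 = 13%. This too is illustration only.

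**Comparison with the symptom study.** If the source study was asked without such a lead-in, which the documents do not show, the ratio of Port Colborne to that study is multiplied by (1 - s). With an assumed true ratio of 1.3 and s = 25%, the observed ratio is 1.3 × 0.75 = 0.98.

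**Comparison of Area 3 with the rest of the city.** If s is the same in both, it cancels from the prevalence ratio. The odds ratio moves slightly towards 1. Take assumed true prevalences of 33.3% and 20%:

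- True odds ratio: (0.333/0.667) / (0.20/0.80) = 2.00.
- With s = 30%, prevalences become 23.3% and 14%, and the odds ratio is (0.233/0.767) / (0.14/0.86) = 1.87.
- The prevalence ratio is 1.67 before and after.

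A false difference between areas, or the masking of a real one, needs s to differ by area, through access to diagnosis or through how interviewers handle the conflict.

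**The case against.** The strongest reply is that the lead-in is only framing. Q1-Q5 are plain questions, open to everyone, and most people asked about a morning cough will simply answer. Other items in the section clearly override the lead-in, such as ever having had a heart attack (Q29) or an adverse pregnancy outcome (Q45). Section 4.2.2.2 has trained nurse interviewers on hand to explain meaning, and section 4.2.2.1 provides a pre-test. The rationale in section 1 mainly names diagnosed respiratory diseases, the sample size in section 6.1.1 rests on asthma and nickel sensitivity, and none of the five symptoms appears in the mock prevalence tables (Tables 5 and 6).

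Much of this stands. It means that s may be close to zero and that the main diagnosed-disease results are not touched. It does not remove the conflict. The protocol tells the nurses nothing about which rule applies to Q1-Q5, and with 24 interviewers planned, different readings are possible. Section 6.2.1.4 still makes symptoms an intended outcome, and section 6.3 still names the comparator.

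Two stronger readings are tempting, and the documents do not support them. A reader might infer that undiagnosed residents are screened out, but there is no skip or eligibility rule. A reader might also infer that "Do you have Gastroenteritis" and "Do you have Jaundice" will yield rates near zero because the lead-in excludes acute episodes. Leaving those out follows from the section's own chronic-condition definition, and nowhere does the protocol say that acute episodes are to be counted. The present-tense wording would miss most past episodes anyway. Section 3.2.2.5 does say "Bilirubin test: validates the jaundice question in the questionnaire", and a long-term diagnosed definition fits a single current blood value poorly. Asking instead about the past 12 months would fit it worse, because jaundice that cleared months earlier need not show on Day 1.

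**Conclusion.** The point holds as a questionnaire design fault confined to Respiratory Q1-Q5. The lead-in conflicts with the items beneath it and with the stated aim of measuring symptoms, and it can lower symptom reporting but not raise it. The size is unknown. Every prevalence shown above rests on assumed p and s, and the result for the external comparison also assumes that the source study had no comparable lead-in. The absolute symptom prevalence and the comparison with that study are the results at risk. Within the city the prevalence ratio is unaffected, and the odds ratio only slightly reduced, unless diagnosis rates or interviewer handling differ by area. The documents do not show that item wording was changed contrary to section 4.2.2.1, nor that the external comparison is invalid. They show only that its basis is weakened for no benefit. The change is worth making because it is almost free now and impossible after the interviews.

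**What to change.** Move the lead-in from the head of the section to directly before Q6 (chronic bronchitis), so that it stays over the chronic-condition items it fits. Open Q1-Q5 with a neutral line such as 'The next questions are about symptoms, whether or not you have seen a doctor'. Leave the wording of Q1-Q5 exactly as borrowed. Use the revised order in interviewer training and in the pre-test.

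The cost is one moved sentence and one added line before the pre-test, with no material increase in interview time. No change to the gastroenteritis or jaundice items is needed for this point.

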1.2.1 CoCs: Toxicology

1.2.1.1 Nickel (Ni)

Nickel is a naturally occurring element that exists mainly in the form of sulphide ores found underground and in silicate minerals found on the surface. In the environment, nickel is found mainly combined with oxygen (oxides) and sulphur (sulfides). Nickel has been shown to be an essential element in certain microorganisms, animals, and plants; and is probably an essential element for humans (ATSDR, 1997).

Nickel is a natural component of the soil. Nickel is also dispersed as particulate dust in the atmosphere due to both human activities (eg. industry) and natural activities (eg. volcanoes). The general population is exposed to nickel via the inhalation of dust, ingestion of food and water, and by contact with objects containing nickel, such as jewelry and coins.

Although the general population is not affected adversely by nickel at typical levels, long-term or high-level exposure to nickel compounds, such as that experienced by workers in nickel refineries or nickel processing plants can negatively impact human health. Some nickel compounds are recognized by the IARC as human carcinogens, notably when present in the upper respiratory tract (nasal passage) and lungs. Chronic nickel inhalation has been linked to respiratory ailments, including asthma and emphysema (Barceloux et al., 1999a; Malo et al., 1982). Moreover, nickel is a well-recognized cause of allergic contact dermatitis in nickel-sensitized individuals (Barceloux et al., 1999a; Shah et al., 1998). Nickel exposure has demonstrated fetal risk (Sunderman

et al., 1980) and spermatotoxic effects (Pandey et al., 1999) in animal studies. In addition, Chashschin et al. (1994) reported an apparent association between maternal employment in a nickel refinery and an increase in risk of adverse pregnancy outcomes (eg. spontaneous abortions, stillbirths, ectopic pregnancy). Further studies, however, are required and are currently being planned by other researchers (Nieboer et al.) to evaluate the specific role of nickel exposure in pregnancy outcome.

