3.2.1.2 Current medical health status

The questions under the Current Medical Health Status section of the questionnaire are designed to help determine the prevalence of specific health conditions. These questions will address a number of specific health areas that have been linked to CoCs exposure or that have been expressed as community concerns. These include health areas relating to respiratory, dermatologic, cardiovascular, thyroid, gastrointestinal, hepatic, neurological, and reproductive questions. These questions come primarily from the Canadian Community Health Survey (CCHS) an existing, validated questionnaire used by Statistics Canada to provide regular and timely cross-sectional estimates of health determinants, health status and health system utilization for 136 health regions across the country. Therefore, much of the data extracted from the Current Medical Health Status section of the questionnaire can be compared to existing data.

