6.2.1.4 Current medical health status

The current medical health status section covers symptomatology, the presence and duration of disease, and information on drug use. Types of diseases assessed fall under categories such as respiratory, upper airway, skin, cardiovascular, thyroid, gastro-

intestinal/liver, neurological, and reproductive health. A question will also be asked about multiple chemical sensitivities.

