6.4 Statistical Analysis

The frequency distributions of variables collected within the health questionnaire and medical tests will be tabulated. The number of missing responses for each variable will be presented, and where possible, these missing values will be treated as a separate category. Particular attention will be given to examining response rates for income levels, since this variable will be used as a proxy to socioeconomic status. If necessary, other factors, such as education, may need to be used instead.

Prevalence rates for health conditions will be calculated by age-group for males and females. Statistically significant differences across strata will be evaluated by using the Chi-Square and likelihood ratio tests for categorical data, and the Student's t-test for continuous data. Multivariate analysis of variance will be used to adjust comparisons for the influence of potential confounding variables. Comparisons will need to take into account possible differences in the age and sex structure of the populations being compared. Of particular interest will be the comparison of Area 3 (otherwise known as the Rodney Street area) to the rest of Port Colborne. Comparisons will also be made to reference data for Ontario or other normative data.

To evaluate the potential influence for response bias, where possible, socio-economic characteristics will be compared between non-respondents and participants. These variables will include: age, sex, family size, income level, and neighborhood of residence. Statistical tests of significance will be performed to determine whether non-responders differed from those who participated in the survey. Response bias will also be examined by comparing survey results obtained from the 1996 Canadian census data.

The prevalence of selected health characteristics will be compared to responses obtained from participants of the 2000 CCHS. In order to control for differences in the underlying populations, direct standardization will adjust for the age and gender make-up of the populations being compared. The ratio of these standardized rates will be calculated, and

95% confidence intervals of this ratio will be used to assess statistically significant differences.

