10.3.3 Instructions Specific to T.R.U.E., Given Post-Application, before Subject Departs

Appendix 10.1: Health Questionnaire

CHAP Health Questionnaire

-  indicates that the questions were derived from the HRQOL-4
 -  indicates that the questions were derived from the 2000 CCHS
 -  indicates that the questions were derived from the Smith-Sivertsen paper
- ADULT indicates adult specific
CHILD indicates child specific

The following information will be kept strictly confidential. Any information that can identify you or your family will be replaced with a unique number (as viewed at the top of this page). This identifying information will be kept separately and under restricted access.

Last Name:  _____

First Name:  _____

Middle Name: _____

Current or Former Resident: **Current / Former**

Number of People in your Household: _____

ALL MEMBERS OF HOUSEHOLD (12+) ARE TO ANSWER THE FOLLOWING QUESTIONS. SOME QUESTIONS MAY NOT APPLY (CHILD OR ADULT SPECIFIC).

Demographic Information

1. What is your date of birth? DD/MM/YYYY 

2. Please indicate your sex: 
 - Male
 - Female

3. People living in Canada come from many different cultural and racial backgrounds.
Are you: 

INTERVIEWER: Read categories to respondent. Mark all that apply.

- 1 ...White?
 - 2 ...Chinese?
 - 3 ...South Asian (e.g., East Indian, Pakistani, Sri Lankan, etc.)?
 - 4 ...Black?
 - 5 ...Filipino?
 - 6 ...Latin American?
 - 7 ...Southeast Asian (e.g., Cambodian, Indonesian, Laotian, Vietnamese, etc.)?
 - 8 ...Arab?
 - 9 ...West Asian (e.g., Afghan, Iranian, etc.)?
 - 10 ...Japanese?
 - 11 ...Korean?
 - 12 ...Aboriginal Peoples of North America (North American Indian, Métis, Inuit / Eskimo)?
 - 13 Other – Specify
-
4. How tall are you without shoes on?  (offer both ways of measuring, want metres)

 5. How much do you weigh?  (offer both ways of measuring, want kg)

6. Do you consider yourself: 
- overweight?
 - underweight?
 - just about right?
7. What is your current marital status?  ADULT
- Married
 - Living Common-law
 - Widowed
 - Separated
 - Divorced
 - Single (never married)
8. Highest grade of elementary or high school completed: 
- ___ Grade 8 or lower (Quebec: Secondary II or lower)
 - ___ Grade 9 – 10 (Quebec: Secondary III or IV; Newfoundland: 1st year of secondary)
 - ___ Grade 11 – 13 (Quebec: Secondary V; Newfoundland: 2nd to 4th year of secondary)
9. Highest degree, certificate or diploma:  ADULT
- ___ No postsecondary degree, certificate or diploma

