Don't Know/Refused (Go to Q42)

41. How old were you when this was first diagnosed?

____ Age in years

(MIN: 0) (MAX: current age)

42. Do you have Parkinson's Disease? 

Yes (Go to Q44)

No (Go to Q44)

Don't Know/Refused

43. How old were you when this was first diagnosed? 
____ Age in years
(MIN: 0) (MAX: current age)

Reproductive Health:

44. Were you ever diagnosed with a fertility problem?
Yes, specify
No
Don't Know/Refused

45. If female, have you ever had any of the following adverse pregnancy outcomes?
1 Spontaneous Abortion/Miscarriage
2 Still Birth
3 Ectopic Pregnancy

Other:

46. Do you suffer from multiple chemical sensitivities? 
Yes
No (Go to Q48)
Don't Know/Refused (Go to Q48)

47. How old were you when this was first diagnosed? 
____ Age in years
(MIN: 0) (MAX: current age)

48. Do you have any other long-term conditions that have been diagnosed by a health care professional? 
Yes
No (Go to Q50)
Don't Know/Refused (Go to Q50)

49. Please specify other long-term conditions. 

Drug Use:

We'd like to ask a few questions about your use of medications, both prescription and over-the-counter.

50. In the past month, did you take: 

a) ... pain relievers such as aspirin or Tylenol (including arthritis medicine and anti-inflammatories)?

Yes

No

R (Go to Mental Health Section)

b) ... tranquilizers such as Valium?

Yes

No

c) ... diet pills such Redux, Ponderal or Fastin?

Yes

No

d) ... anti-depressants such as Prozac, Paxil or Effexor?

Yes

No

e) ... codeine, Demerol or morphine?

Yes

No

f) ... allergy medicine such as Seldane or Chlor-Tripolon?

Yes

No

g) ... asthma medications such as inhalers or nebulizers?

Yes

No

h) ... cough or cold remedies?

Yes

No

i) ... penicillin or other antibiotics?

Yes

No

j) ... medicine for the heart?

Yes

No

k) ... medicine for blood pressure?

Yes

No

l) ... diuretics or water pills?

Yes

No

m) ... steroids?

Yes

No

n) ... insulin?

Yes

No

o) ... pills to control diabetes?

Yes

No

p) ... sleeping pills?

Yes

No

q) ... stomach remedies?

Yes

No

r) ... laxatives?

Yes

No

If female & age ≤ 49 ,

s) ... birth control pills?

Yes

No

If female & age ≥ 30 ,

t) ... hormones for menopause or aging symptoms?

Yes

No

DK, R

t.1) What type of hormones are you taking?

INTERVIEWER: Read categories to respondent.

- 1 Estrogen only
- 2 Progesterone only
- 3 Both
- 4 Neither

t.2) When did you start this hormone therapy?

|_|_|_| Year

(MIN: year of birth + 30) (MAX: current year)

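### Q45 asks about adverse pregnancy outcomes but no item records pregnancy history, so risk among ever-pregnant women cannot be estimated and comparisons would mix childbearing with risk

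*Protocol*

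**What the plan says.** The health questionnaire in Appendix 10.1 opens with the instruction "ALL MEMBERS OF HOUSEHOLD (12+) ARE TO ANSWER THE FOLLOWING QUESTIONS", and adds that some questions are specific to adults or children. Under Reproductive Health it has two items. Q44 reads "Were you ever diagnosed with a fertility problem" and offers yes, no and don't know/refused. Q45 reads "If female, have you ever had any of the following adverse pregnancy outcomes" and offers three outcomes only: miscarriage, stillbirth and ectopic pregnancy. Q45 has no adult-only marker.

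Section 3.2.1.2 describes this part of the questionnaire as "designed to help determine the prevalence of specific health conditions" and includes reproductive questions. Section 6.2.1.4 names the disease areas assessed, among them "intestinal/liver, neurological, and reproductive health". Section 1.2.1.1 gives the background: one cited study "reported an apparent association between maternal employment in a nickel refinery and an increase in risk of adverse pregnancy outcomes", with the same three events as examples.

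On analysis, section 6.4 says "Prevalence rates for health conditions will be calculated by age-group for males and females" and names Area 3 against the rest of Port Colborne as the comparison of particular interest. It states no denominator for Q45.

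**The concern.** Miscarriage, stillbirth and ectopic pregnancy can happen only to a woman who has been pregnant, and the chance of ever having had one rises with the number of pregnancies. To read such an outcome as a risk, one must know who was ever pregnant and preferably how often. If the form does not record this, a proportion among all females is the product of two things: how many women have been pregnant, and how often pregnancy went wrong. Two areas, or two metal-exposure groups, could then differ because of family size or timing of childbearing alone.

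This is a matter of data collection, so it has to be settled before the questionnaire goes into the field. Section 4.5 says the link between identifier and identity will be erased once the data are validated. After that, women could not be asked again.

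**Working it through.** **1. Can pregnancy history be rebuilt from other items?** The items in Appendix 10.1 that might bear on it are:

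- Q44, fertility problem: does not record pregnancies.
- Q50 s and t, birth control pills and menopausal hormones: past-month use only.
- Marital status and household size: neither identifies past pregnancies.
- Current pregnancy: asked about only as an exclusion from the patch test (section 4.1.1.1.2 and Appendix 10.3); says nothing about the past.

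No item gives ever-pregnant status, number of pregnancies or live births. All females is the only denominator available.

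**2. Formula.** The protocol states no prevalence or power for these outcomes, so there is no figure of its own to reproduce. Let *g* be the share of females ever pregnant and *r* the risk of at least one listed outcome among ever-pregnant women. Then

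prevalence over all females: *p* = *g* × *r*

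odds ratio between areas: [*p*₁/(1 − *p*₁)] / [*p*₂/(1 − *p*₂)]

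The values of *g* and *r* below are assumptions. No age adjustment is applied.

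**3. One population.** With *r* = 0.20 and *g* = 0.60, 0.70 and 0.80, *p* = 0.12, 0.14 and 0.16.

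**4. Two areas, equal true risk (*r* = 0.20 in both, true odds ratio 1.00).**

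| *g*₁ vs *g*₂ | *p*₁ vs *p*₂ | Odds ratio, all females |
|---|---|---|
| 0.70 vs 0.70 | 0.14 vs 0.14 | 1.00 |
| 0.80 vs 0.70 | 0.16 vs 0.14 | 1.17 |
| 0.85 vs 0.70 | 0.17 vs 0.14 | 1.26 |
| 0.85 vs 0.65 | 0.17 vs 0.13 | 1.37 |
| 0.60 vs 0.75 | 0.12 vs 0.15 | 0.77 |

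For the third row: (0.17/0.83)/(0.14/0.86) = 0.2048/0.1628 = 1.26; the prevalence ratio is 0.17/0.14 = 1.21.

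**5. Two areas, true odds ratio 2.0 among ever-pregnant women.** With *r*₂ = 0.20 the odds are 0.25; doubled they are 0.50, so *r*₁ = 0.50/1.50 = 0.333.

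| *g*₁ vs *g*₂ | *p*₁ vs *p*₂ | Odds ratio, all females |
|---|---|---|
| 0.70 vs 0.70 | 0.233 vs 0.140 | 1.87 |
| 0.60 vs 0.75 | 0.200 vs 0.150 | 1.42 |
| 0.80 vs 0.70 | 0.267 vs 0.140 | 2.23 |

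The risk signal survives, but it is shifted by an amount the data cannot reveal.

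**6. What age adjustment does.** The same formula holds within an age band. If *g* differs between areas only because their age structures differ, it is equal within bands and the adjusted odds ratio under equal risk returns to 1.00. If women of the same age differ in childbearing, the distortion stays, with the within-band shares in place of the crude ones. The protocol gives nothing from which to size that remainder.

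**The case against.** Several points on the other side are sound.

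- **No denominator is stated.** A reader might infer that the plan has chosen to count these outcomes over all females. It has not said so; that follows only from what the form collects. Mock Tables 5 and 6, which list the conditions to be compared by area and with Ontario, contain no adverse pregnancy outcome. Section 6.4 plans metal models for selected health conditions without naming this one. Any comparison rests on the general wording of 6.4.
- **The all-female proportion is a legitimate description.** The primary objective in section 2.0 is to characterize current health status, and the share of female residents with such a history is a valid quantity. It is too low only if read as the risk among women who have been pregnant, which the protocol nowhere promises to estimate.
- **Childbearing does not replace risk.** A reader might conclude that an area comparison would reflect childbearing instead of risk. Step 5 shows otherwise, and with equal shares there is no bias under equal risk.
- **Adjustment and age grouping help.** Prevalence is planned by age group, so girls need not dilute the adult rows. Mock Table 5 adjusts for age and sex, and sections 3.3 and 3.3.1 add other confounders, including socio-economic status.
- **Unanswered items are marked.** A reader might infer that a skipped Q45 looks the same as no event. Under section 5.1 the interviewer initials unanswered questions, under 4.2.2.2.2 a coordinator checks for missing data, and 6.4 reports missing responses. That largely answers the worry.
- **The nickel question is partly assigned elsewhere.** Section 1.2.1.1 goes on to say that other researchers are planning studies of nickel and pregnancy outcome.

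These points lower the stakes. They do not supply the missing history: a woman never pregnant still cannot be told from one pregnant without an event.

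**Conclusion.** The point holds as a gap in data collection. Q45 gathers the events without the pregnancies, so the form supports one quantity only: the proportion of all females aged 12 and over with a history of a listed outcome. Risk among ever-pregnant women and risk per pregnancy cannot be estimated, and a later analysis plan cannot repair this.

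If the outcome is compared by area or metal level, childbearing and risk are mixed. With equal true risk of 20% and the assumed unequal shares above, the crude odds ratio runs from 0.77 to 1.37, with 1.26 for 85% versus 70%. It is 1.00 when the shares are equal. These figures rest wholly on assumed shares and risk, before age adjustment, and the protocol gives no evidence that the areas differ in childbearing at a given age. They show what could happen and are not an estimate of bias. The documents do not support the claim that a specified analysis is wrong. The change is a cheap improvement to one item.

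**What to change.** In Appendix 10.1, before Q45, add an item asking whether the woman has ever been pregnant, with a skip past Q45 if not, and an item asking how many pregnancies she has had. In Q45, record the number of each outcome and add codes for none and for don't know/refused. In section 6.4, add a sentence that these outcomes are reported among ever-pregnant women, or per pregnancy with the number of pregnancies as denominator, and that any area or metal model for them uses the same denominator. A per-pregnancy analysis should allow for several pregnancies in the same woman.

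The cost is two short items, under a minute of interview time, and an update of the stated count of 104 questions. Section 4.2.2.1 commits to unchanged wording for borrowed questions, but Q45 carries no source marker in Appendix 10.1, so comparability with other surveys is not lost. The pre-test described in that section can cover the new items. For adolescents, section 4.2.4.2.2 already has parents wait outside during the interview.
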